## RESEARCH PLAN

### Specific Aims

African Americans (AA) are at increased risk for dementia-related diseases and experience significant differences in diagnosis and other health outcomes regarding dementia and dementia care (e.g., Bonds & Lyons, 2018), including delayed dementia diagnosis and treatment. Along the chronic disease continuum of care, early screening is one of the first critical steps to reduce diagnosis delays. However, AA experience many multi-layered barriers to dementia screening and follow-up services including limited access to care, mistrust of health professionals, dementia-related stigma, and limited cultural appropriateness of dementia services (Bonds & Lyons, 2018; Epps et al, 2018). Despite growing calls to increase the reach of dementia screening in nonmedical settings with older adult AA to address disparities, no screening studies exist using culturally-tailored approaches in AA community settings, particularly AA churches.

AA churches have extensive influence and reach in Black communities, high attendance rates especially among older adults, strong emphasis on health, and outreach ministries that serve community members who may be at greatest risk for dementia (e.g., Pew Forum on Religion and Public Life, 2009; Pew Research Center, 2015; Taylor et al, 2004; Berkley-Patton et al., 2012). Our AA church-based pilot and RCT health screening studies have demonstrated: a) church leaders can and will expertly deliver screening interventions using prepackaged, supportive tools, b) tailored tools and church-based screening were highly acceptable/feasible and increased reach to church members and community members using outreach services, and c) use of this approach and such toolkits significantly increased screening for highly stigmatized diseases, including HIV and other sexually transmitted diseases (Berkley-Patton et al., 2010, 2013, 2016, 2018a). We also established that AA churches can reach high risk groups, including older adults with low levels of education, income, and insurance, and who suffer from diseases (e.g., diabetes, heart disease) that put them at greater risk (Berkley-Patton et al., 2018b).

The **primary aim** of this study is to conduct an exploratory pilot study to examine feasibility and outcomes of a culturally/religiously-tailored church-based dementia screening intervention among older adult AA church members and community members who use church outreach services in 2 AA churches (N=100). Our secondary outcomes are dementia-related stigma and linkage to care (LTC). Intervention *content* is based on the Theory of Planned Behavior (TPB), intervention *delivery* is based on the Social-Ecological Model (Ajzen, 1991; Bronfenbrenner, 1979) – both guided by a faith community engagement approach. Trained faith leaders will deliver the tailored intervention through multilevel church outlets: individual self-help resources (e.g., risk checklist, commitment to screening cards); group ministry discussion guides about dementia; church-wide services using sermon guides, responsive readings, and church bulletin inserts; and church-community level text messages, dementia screening, and linkage to care services. Two screening events will be held at each church. We will also conduct a process evaluation that will include post-test study focus groups.

**Specific Aim 1.** Test a religiously/culturally-tailored, church-based dementia screening intervention on **receipt of dementia screening**, stigma, and LTC use among an older adult AA church-populations at 4 months.

**Hypothesis.** The tailored church-based dementia screening intervention will evidence increased screening and LTC rates, and lower dementia-related stigma beliefs at 4 months.

**Specific Aim 2.** Evaluate predictors of receipt of dementia screening at 4 months among older adult AA church-populations to determine modifiable screening facilitators/barriers.

**Specific Aim 3.** Conduct a process evaluation to examine study intervention implementation facilitators, barriers, and dose along with exposure and satisfaction to identify essential intervention components.

Developing culturally-tailored approaches to address this disparity will permit earlier dementia diagnosis, assist in eliminating disparities and provide timely opportunities to make lifestyle changes and take advantage of available treatment, make appropriate plans, seek support from family and friends, and maintain a desired quality of life for as long as possible. Findings from this study could provide a feasible, acceptable, sustainable dementia screening and LTC approach for older adult AA church-affiliated populations in faith community settings. Findings could contribute to understanding how to increase the capacity of AA churches to assist delivering and improving use of dementia services with underserved AA populations, and thereby assist in reducing dementia AA health disparities.

## Significance

African Americans (AA) have double the risk of developing dementia as whites. Dementia risk factors include diabetes, smoking, poor diet, obesity, hypertension, physical inactivity, and depression (e.g., Crous-Bou et al., 2017; Deckers et al., 2018, Baumgart et al., 2015) – health conditions that significantly burden AA. AA are also diagnosed later in the disease than their white counterparts (Gleason et al., 2017). These disparities put older AA with cognitive impairment at risk for a variety of negative health outcomes such as falls, malnutrition, frailty, dehydration, and mortality (Fogg et al., 2017, 2018; Blackwood & Martin, 2017) because they do not receive disease-relevant supports for maintaining their health.

Past research suggests that a critical step in addressing unmet dementia care needs is to improve capacity for early dementia screening in primary care (e.g., Tan et al., 2016) and in the community (e.g., Han et al. 2013). Despite continued calls for earlier screening of AA (e.g., Goldstein et al., 2014; Grober et al., 2016, Jackson et al., 2017), many screening barriers exist for AA – and are multilayered. These include limited access to dementia information and screening (e.g., Epps, 2018), stigma associated with cognitive decline (e.g., Epps, 2018; Gleason et al., 2016; Gupta et al., 2016; Tappen et al., 2011), and mistrust of healthcare professionals to consider AA cultural needs (e.g., Bond & Lyons, 2018). In addition, only half of those who screen positive receive follow-up care (Dale et al., 2008). There is great need to increase acceptable and accessible dementia screening as well as timely *linkage to care (LTC)* to improve access to dementia services and confront disparities.

Dementia intervention studies with AAs are slowly beginning to appear in the literature (e.g., Cothran et al., 2017; Owusu et al., 2019; Rovner et al., 2018). For example, Cothran et al. reported that a physical activity intervention for AA caregivers of family members living with dementia successfully reduced caregiver subjective burden. Rovner et al. (2018) found that a culturally-tailored intervention focused on behavioral activation (e.g., social, cognitive, and physical activity) slowed cognitive decline in AA older adults with mild cognitive impairment. This study indicated the inclusion of cultural aspects (social relationships, spiritual/religious activities) as key activators. These studies highlight the need for tailoring materials and strategies to AA, including social support and religiosity, to improve acceptability and impact of such interventions. However, none of these studies have addressed dementia screening with older adult AA. *Our pilot intervention will address screening barriers with culturally-appropriate strategies in AA church settings to enhance screening acceptability and accessibility.*

AA churches are highly influential institutions that have many untapped strengths to extend the reach, influence, and impact of dementia screening interventions with older adult AA. For example, AA churches have high attendance rates, especially among older adults, strong emphasis on health, provide highly valued social support from fellow church members, and include outreach ministries that serve community members who may be at greatest risk for dementia. Thus, AA churches are well-positioned to serve church and community members who might benefit most from dementia education, early screening, and LTC opportunities.

Additionally, past research has demonstrated that the AA church can be a practical setting for health screening interventions with older adult AA (e.g., Campbell et al., 2007). Critical intervention components in AA church studies have included church leaders' delivery of culturally/religiously-tailored health messages via naturalistic church activities (e.g., sermons, testimonials, ministry group meetings). Our own past church-based studies have demonstrated older adult AA are highly represented (> 40%) and believe the church plays an important role in providing health services (Berkley-Patton et al., 2018a). *We will engage faith leaders in implementing our proposed intervention using culturally-religiously tailored materials/activities packaged in a supportive, church-based Dementia Screening and Compassion Tool Kit.*

## Innovation

To our knowledge, no community-based, culturally and religiously-tailored dementia screening intervention studies have been conducted with older adult AA in their churches. Our church-based dementia screening and LTC intervention study is innovative and fills gaps in the literature by:

- 1) being the first to study dementia screening, including related risk factors, and LTC among AA church populations;
- 2) uniquely including community members using church outreach services (e.g., food/clothing programs, social services) – an underserved population with limited access to health services;

- 3) being the first to use a culturally/religiously-tailored Dementia Screening and Compassion Tool Kit with content designed to encourage dementia screening, reduce stigma, be socio-ecologically and theoretically-grounded, and be delivered by church leaders;
- 4) using a multilevel approach for intervention delivery via peer-to-peer, group ministries, church-wide services, and community level church outlets; and
- 5) using religiously-tailored text messages to increase reach of screening messages with church-community members.

## **Approach**

Our pilot religiously-tailored dementia screening intervention will assess feasibility (e.g., intervention implementation dose, exposure, satisfaction, facilitators/barriers) and outcomes (self-report and objective receipt of screening and LTC; stigma) with 100 older adult AA members in 2 AA churches. The primary outcome measure will be receipt of screening (self-reported and objectively assessed) at 4 months. Guided by the Theory of Planned Behavior (TPB) and a socioecological approach, we will produce a culturally and religiously tailored intervention package appropriate for the AA church-context and delivered through multilevel church outlets. We will engage our highly active KC FAITH Community Action Board led by Calvary Community Outreach Network (CCON) in the development of the intervention components, including the Dementia Screening and Compassion Tool Kit to ensure cultural-religious appropriateness for AA churches. Our team has extensive experience in developing, implementing, and sustaining culturally-religiously tailored, church-based AA health promotion interventions using TPB and socio-ecological approaches guided by faith community-engagement (Berkley-Patton et al., 2010, 2013, 2016, 2018a, b, c; Moore et al, 2016). Our team also has extensive experience in conducting large-scale recruitment and data collection activities in church settings, especially before, during, and after Sunday morning services and during church outreach activities (Berkley-Patton, 2010, 2016, 2018a, 2018b, 2018c).

**Setting and participants.** Two AA churches in the Kansas City, MO urban area will participate and have already provided letters of support. Criteria for church participation includes: a) a minimum of 150 adult church members who regularly attend Sunday services; b) an active church outreach ministry (e.g., food/clothing pantry, social services, daycare); c) commitment from the pastor and two *church health liaisons (CHLs)* to assist in study activities; and d) commitment to hold 2 dementia screening/LTC events over 4 months. Impact will be tracked among 50 church and community member participants from the two participating AA churches, for 100 participants total. Church members will be recruited by study staff who provide study information during church services and flyers in participating churches. Community members will be recruited similarly during churches' outreach ministries. Participants will: a) identify as AA, b) be aged > 50; and c) regularly attend church (>once a month) or use church outreach services (3-4 times per year). Prior screening will not be an exclusion for participation. Anyone will be able to receive free screening, regardless of their participation in the study. Participants will complete baseline and 4-month follow up surveys.

**Intervention implementation.** Pastors, CHLs, and KC CARE Health Center (our health agency partner; see letter of support) community health workers (*CHWs*) will participate in a pre- and midpoint training on study manualized implementation information, procedures, and brain health. The trainings will also be used to review the Dementia Screening and Compassion Tool Kit materials/activities and plan/schedule delivery of activities in targeted, multilevel church services and ministries. The project team will host an informational presentation in the churches on brain health and the importance of screening for dementia and cognitive impairment as part of a church-hosted project-prescribed Kick-off event to launch intervention implementation. Pastors and church health liaisons will deliver 2 to 3 toolkit items per month over a 4-month period through multilevel church outlets, including: a) self-help materials (e.g., educational brochures, risk checklist, screening commitment cards) (individual level); b) discussion guides (ministry group level); c) sermon guides, responsive readings, testimonials, and church bulletins (church level); and d) screening via UMKC psychology students and faculty and linkage to care (e.g., referral for diagnostic evaluation, linkage to community resources) via trained community health workers (church-community level). Two screening events will be held in each church, at 4 weeks and 12 weeks. UMKC psychology faculty and trained students will conduct the screening and provide immediate feedback via electronic-tablets.

**Measures.** We will assess self-reported receipt of screening (ever/past year and where/why screening received). A battery of assessments will be administered including the AD8 (Galvin et al., 2007) for dementia screening, the LIBRA Index to assess modifiable risk factors (Schiepers et al., 2017), the Lubben Social

Network Scale (Lubben et al., 2006) to assess social engagement, the Physical Activity Scale for the Elderly (PASE, Washburn et al., 1993) to assess healthy lifestyle factors, the Duke University Religion Index (Koenig & Bussing, 2010) to assess religious behaviors, the RCOPE (Pargament et al., 2011) to assess religious coping, and the Perceptions Regarding Investigational Screening for Memory in Primary Care (PRISM-PC; Boustani et al., 2008) and the Stigma Impact Scale (Fife & Wright, 2000 as modified for use with dementia by Burgener & Berger, 2008) to assess perceived dementia-related stigma. We will also assess depression using the PHQ9. Demographic factors (e.g., age, education, occupation, marital status) and chronic health conditions (e.g., diabetes, high blood pressure) will be assessed. For our process evaluation, we will assess intervention implementation with CHLs and intervention exposure/satisfaction with participants. All measures will be assessed at baseline and 4 months. We will conduct post-study focus groups with 24 participants to obtain feedback on study materials/procedures and refine study design/delivery for future projects.

**Data analysis.** Self-reported receipt of screening (Yes/No) is our primary outcome. We will also collect objective data on persons screened. Stigma and LTC use are secondary outcomes. To explore pilot study outcomes and hypothesized pathways with baseline/4-month comparisons, we will use frequencies (ns), percentages, and means/SDs. Referrals to care and actual care received will be documented using CHW objective records. Logistic regression analyses with demographic and psychosocial variables, including TPB, will be conducted to determine associations with receipt of dementia screening screen and LTC use. Linear regression will be conducted to examine stigma associations. Perceived acceptability of study intervention materials/process and feasibility/challenges will be assessed in our post-study focus groups. Together, this information will provide a strong basis for designing a larger, randomized study of dementia screening in African American churches. Power calculations will not be conducted since this is an exploratory pilot study.

**KUADC resource utilization.** We anticipate using the Outreach and Recruitment (OR) Core to tap the Core's experience in community education on the latest research in brain health and dementia. As described here, part of our project is to increase knowledge about AD and other dementias in the African-American community, which can then support our efforts to increase screening and linkage to care. As we pursue this work, the OR Core will help us build a network of colleagues and collaborators for future research projects.

**Dissemination of findings and plans for additional funding.** We will prepare presentations and at least 5 scholarly publications focused on study development, baseline findings, primary/secondary outcomes, process evaluation, and screening predictors. We plan to use study findings to support a future clustered, RCT NIH application and address feasibility, acceptability, and statistical power to detect a change in screening rates. Our project fits well with NIH priorities. There is a new Program Announcement ([PA-18-932](#)) titled "Increasing Uptake of Evidence-Based Screening in Diverse Adult Populations (R01 Clinical Trial Optional)". This funding opportunity "invites applications that seek to understand strategies to reduce disparities in the uptake of evidence-based screening across the adult lifespan in diverse clinical and community settings, and/or with traditional, non-traditional and/or allied health care providers". We plan to submit to this PA, June 2020 cycle.

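### The Yes/No screening outcome is not limited to screening after baseline, so the 4-month rate can include screening received before the study

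*Combined protocol and SAP*

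**What the plan says.** All references are to the combined protocol and SAP.

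- **Outcome.** Approach, Data analysis: "Self-reported receipt of screening (Yes/No) is our primary outcome". The opening paragraph of Approach words it differently: "The primary outcome measure will be receipt of screening (self-reported and objectively assessed) at 4 months". Data analysis treats the objective record as an addition: "We will also collect objective data on persons screened".
- **Item.** Approach, Measures: "We will assess self-reported receipt of screening (ever/past year and where/why screening received". No other recall window appears in the document.
- **Entry.** Approach, Setting and participants, admits people who have already been screened and opens the free screening to non-participants as well.
- **Timing.** The timeline section puts the baseline survey in week 0, screening events in weeks 4 and 12, and the follow-up survey in week 16.
- **AD8.** Measures: "A battery of assessments will be administered including the AD8". The AD8 is the one instrument there whose stated purpose is to screen for dementia. The same paragraph adds: "All measures will be assessed at baseline and 4 months".
- **Use.** Data analysis describes the outcome "To explore pilot study outcomes and hypothesized pathways with baseline/4-month comparisons" and makes it the dependent variable of a logistic regression on demographic and psychosocial variables. The Aim 1 hypothesis reads: "The tailored church-based dementia screening intervention will evidence increased screening and LTC rates".

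**The concern.** The study wants to know how many people are screened once the church programme starts. The item instead asks whether they were screened ever, or in the past year. The plan does not say which window makes the Yes, and neither window starts at baseline. Someone screened in a clinic six months before enrolment, who attends neither church event, is a correct Yes at week 16 under both windows.

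Three uses of the variable are affected: the 4-month rate, the baseline/4-month change, and the Aim 2 regression. In the regression, people screened only before the study are coded as screened, so a predictor can reflect past access to care instead of response to the programme. The Dissemination paragraph says the findings will inform power for a later cluster-randomised trial, so a misread rate would carry forward.

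Two smaller gaps concern the same definition. The plan does not say whether an AD8 given in a study survey counts as having been screened. It also gives two accounts of whether objective data belong to the primary outcome.

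**Working it through.** The plan has no power calculation or expected rate to reproduce. Its sample size is consistent: 2 churches x 50 = 100.

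**1. Window at week 16.** A 52-week recall covers 16 study weeks and 52 - 16 = 36 earlier weeks. So w = 36/52 = 0.692 of the window is pre-study and b = 16/52 = 0.308 is study time. The ever window has no lower limit.

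**2. Rate at 4 months.** Let u be the true proportion screened since baseline, and q the proportion already screened at baseline within the window used. Lifetime and past-year q are different quantities, and lifetime q cannot be the smaller. Neither u nor q is in the documents; both are assumed. With accurate recall and u independent of q:

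- ever rate = u + q(1 - u), an excess of q(1 - u)
- past-year rate = u + wq(1 - u), an excess of wq(1 - u), if earlier screens are spread evenly over the year

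Excess over u in percentage points (ever / past year), each read at its own q:

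| q | u = 20% | u = 40% | u = 60% |
|---|---|---|---|
| 5% | 4.0 / 2.8 | 3.0 / 2.1 | 2.0 / 1.4 |
| 10% | 8.0 / 5.5 | 6.0 / 4.2 | 4.0 / 2.8 |
| 20% | 16.0 / 11.1 | 12.0 / 8.3 | 8.0 / 5.5 |
| 30% | 24.0 / 16.6 | 18.0 / 12.5 | 12.0 / 8.3 |

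Without independence, at u = 40% and q = 20%, the ever rate can lie anywhere from 40% (everyone previously screened is rescreened) to 60% (none is). The past-year range is 40% to 40 + 0.692 x 20 = 53.8%.

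For scale, the 95% margin on a 40% rate with N = 100 is 1.96 x sqrt(0.4 x 0.6/100) = 9.6 points, ignoring clustering by church and dropout. At u = 40%, the excess at q = 5-10% falls inside that margin. The ever excess at q = 20-30% (12-18 points) exceeds it.

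**3. Baseline/4-month change.** At u = 40% and q = 20%, with independence and one earlier screen per person:

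- Ever: u(1 - q) = 0.40 x 0.80 = 32.0 points. This is first-time screening only.
- Past year, earlier screens evenly spread: u + wq(1 - u) - q = 0.483 - 0.200 = 28.3 points. Comparing the 16 weeks before baseline with the 16 weeks after gives u - bq = 0.400 - 0.062 = 33.8 points. The gap is wqu = 0.692 x 0.20 x 0.40 = 5.5 points. It comes from people screened in the study who were already Yes. The loss bq from screens leaving the window appears in both figures and cancels.
- Past year, all earlier screens in the 16 weeks before baseline: 0.52 - 0.20 = 32 points, against a matched 0.40 - 0.20 = 20 points.

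The past-year change can therefore fall below or above the matched comparison, depending on when earlier screens took place.

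**4. Aim 2 illustration.** Take a factor with no effect on uptake (40% in both groups) but lifetime prior screening of 10% against 30%. The ever outcome is 46% against 58%, and the odds ratio is (0.58/0.42)/(0.46/0.54) = 1.62 instead of 1.00. With 50 per group, SE(log OR) = sqrt(1/23 + 1/27 + 1/29 + 1/21) = 0.403, a 95% interval of about 0.74 to 3.57. If 10% and 30% are instead past-year prevalences, evenly spread, the past-year outcome is 44.2% against 52.5%, odds ratio 1.40.

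**The case against.** The strongest defence is that the plan already collects what is needed. It asks where and why screening was received, records persons screened objectively, fixes the event dates, and measures screening status at baseline. The first-time screening shown by the ever change is also a legitimate quantity. All of this stands, and it makes the repair cheap. But no rule uses this material to define Yes, and step 3 shows that the baseline comparison does not return uptake. The 4-month wording in the plan sets the time of assessment, not a recall window.

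It is also fair that every size above is assumed, and that the error vanishes if nobody was screened before or all such people are rescreened.

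Three stronger readings are tempting, and the documents do not support them:

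- A reader might infer that the past-year change always understates a matched comparison because old screens drop out of the window. Step 3 shows that neither the direction nor that mechanism holds in general.
- A reader might infer that the baseline AD8 produces a false increase of known size, or a rate near 100%. The text does place the AD8 at baseline, so some participants could report it. But Intervention implementation describes screening as separate events with tablet feedback, and the plan nowhere says the survey AD8 counts. The size of any miscount is unknown.
- A reader might compare the two figures in each cell of the step 2 table as if they came from one population. They do not, because q has a different meaning in each.

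**Conclusion.** The point holds as a gap in the primary outcome definition. That no passage limits Yes to screening after baseline is certain from the text. Given accurate recall, the 4-month rate is at or above study-period uptake, and strictly above when some participants were screened earlier within the window and not again. The excess is about 2-24 points (ever) or 1-17 points (past year) over the assumed ranges in step 2, under independence and, for past year, evenly spread earlier screens. The direction of error in the past-year change cannot be stated in advance.

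The AD8 question is secondary and unquantified. The two accounts of the objective data need one reconciling sentence.

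This should be fixed, but it is not fatal. The study is an exploratory pilot with descriptive comparisons and no power calculation. What is at stake is the reading of a rate and of the Aim 2 estimates, including their use in planning the next trial. A reader might infer that the plan risks a false-positive test; the wide interval in step 4 points to bias in an estimate instead.

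**What to change.** 1. At week 16, define Yes as dementia or memory screening received after the participant's baseline survey date, and print that date in the item.
2. State that an AD8 given as part of a study survey does not count, and that screening at a church event does. Check replies against the event log matched to participant ID, which is needed because the events are open to anyone, or against the reply on where screening took place.
3. State in one sentence whether self-report or the objective record is primary, so that the opening of Approach and Data analysis agree. Report the other alongside it.
4. Keep baseline ever and past-year status as a descriptor and as an Aim 2 covariate.
5. Optional, if a before/after comparison is wanted: at baseline, before the AD8, ask about the preceding 16 weeks. Read the change as uptake net of background screening.

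The cost is one reworded item, matching the log to participant IDs, and two or three sentences in the outcome definition, plus one baseline item if step 5 is adopted. No extra participants or visits are needed.

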## Overview of primary intervention activities and timeline

Week 01: Study implementation training with pastor, CHLs, an CHWs

Week 02: Recruitment information via flyers and church bulletin information is distributed in churches

Week 03: Study introduced by study team in Sunday morning services and in outreach ministry activities, volunteering church and community members are consented, and baseline survey is administered

Week 1: Intervention Kick-off: Informational presentation on brain health and dementia screening; pastoral sermon, responsive reading, and risk checklist delivered during Sunday morning service

Week 2 – 12: Pastors and CHLs deliver dementia toolkit items to encourage screening and reduce stigma

Week 4: First screening event with linkage to care services is held

Week 7: Refresher study implementation training with pastor, CHLs and CHWs

Week 12: Second screening event with linkage to care services is held

Week 16: 4-month follow-up survey is administered

Weeks 18: Focus groups with participants and CHLs are conducted

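### The plan does not say whether self-report or the event record decides who was screened, so reporting error can bias uptake and the Aim 2 associations

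*Combined protocol and SAP*

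**What the plan says.** The outcome is defined twice. The opening paragraph of the Approach says "The primary outcome measure will be receipt of screening (self-reported and objectively assessed) at 4 months". The Data analysis paragraph says "Self-reported receipt of screening (Yes/No) is our primary outcome" and follows it with "We will also collect objective data on persons screened", giving those objective data no stated role in the analysis.

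On the survey item, Measures says "We will assess self-reported receipt of screening (ever/past year and where/why screening received". On timing, the church events are at weeks 4 and 12, and the timeline lists "Week 16: 4-month follow-up survey is administered". The toolkit includes "self-help materials (e.g., educational brochures, risk checklist, screening commitment cards) (individual level", and the timeline places the risk checklist in the week-1 Sunday service. Measures also puts the AD8, described as a dementia screen, in the assessment battery, and all measures are taken at baseline and 4 months.

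Aim 2 is to "Evaluate predictors of receipt of dementia screening at 4 months among older adult AA church-populations to determine modifiable screening facilitators/barriers". The model is described as "Logistic regression analyses with demographic and psychosocial variables, including TPB, will be conducted to determine associations with receipt of dementia screening screen and LTC use". Neither statement names the source of the receipt variable.

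**The concern.** With two sources and no rule for disagreement, the analyst must choose after seeing the data, and the Data analysis wording points to self-report. Self-report can fail in two ways here. A participant who attended an event may not remember it 12 or 4 weeks later, and poorer memory makes that more likely. A participant who attended no event may answer Yes because of the risk checklist or the AD8 in the survey. On a plain reading every participant meets the AD8 at baseline, so that Yes could even be truthful under a loose definition.

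If either error varies with cognition, or with age, education or depression as its correlates, it biases the uptake percentage. It can also produce an association in Aim 2 that reflects reporting rather than access, such as an apparent failure to reach people with cognitive concerns. These results are meant to travel: the dissemination section plans papers on primary outcomes and on screening predictors, and a cluster-randomised application that addresses power to detect a change in screening rates. This concern would remain with a perfectly worded look-back window and complete survey return.

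**Working it through.** The plan gives no power, alpha, effect size or reporting accuracy, so there is no figure of its own to reproduce. From the documents come N = 100, events at weeks 4 and 12, and the survey at week 16. The recall gaps are 16 - 4 = 12 weeks and 16 - 12 = 4 weeks. Every uptake, recall and false-Yes rate below is an assumption.

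**Formula.** Reported rate = uptake x recall + (1 - uptake) x false-Yes rate, applied within each AD8 group. True uptake is equal in the two groups, so the true odds ratio is 1.0.

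**Forgetting only.** Uptake 60%, no false Yes, 20% AD8-positive. AD8-negatives at 95% recall report 0.60 x 0.95 = 0.570, odds 0.570/0.430 = 1.326.

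| Recall, AD8-positive | Reported, AD8-positive | Pooled (0.8 x 0.570 + 0.2 x reported) | Odds ratio |
|---|---|---|---|
| 85% | 0.60 x 0.85 = 0.510 | 0.558 | (0.510/0.490)/1.326 = 0.79 |
| 75% | 0.60 x 0.75 = 0.450 | 0.546 | (0.450/0.550)/1.326 = 0.62 |
| 60% | 0.60 x 0.60 = 0.360 | 0.528 | (0.360/0.640)/1.326 = 0.42 |

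Reported uptake is 4 to 7 points low. Three of those points come from the 95% recall in the AD8-negative group (0.600 - 0.570 = 0.030).

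**False Yes added.** Uptake 40%, 20% of unscreened people answering Yes, recall 95% and 75%. AD8-negatives: 0.40 x 0.95 + 0.60 x 0.20 = 0.50. AD8-positives: 0.40 x 0.75 + 0.60 x 0.20 = 0.42. Pooled: 0.8 x 0.50 + 0.2 x 0.42 = 0.484. A true 40% is now reported as 48%, so the bias in the percentage has changed sign.

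**Direction of the odds ratio.** Take true uptake of 30%, with recall and specificity both 95% in the cognitively intact: 0.30 x 0.95 + 0.70 x 0.05 = 0.32.
- If the lower-cognition group differs only by a 25% false-Yes rate, it reports 0.30 x 0.95 + 0.70 x 0.25 = 0.46, and the odds ratio is 1.81.
- If it has 75% recall and a 15% false-Yes rate, it reports 0.225 + 0.105 = 0.33, and the odds ratio is 1.05. The errors nearly cancel.

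**Through a correlate.** AD8 is not a listed covariate. Suppose one education group is 30% AD8-positive and the other 10%, with the forgetting-only rates above. At 60% recall the groups report 0.7 x 0.570 + 0.3 x 0.360 = 0.507 and 0.9 x 0.570 + 0.1 x 0.360 = 0.549, odds ratio 0.84. At 85% recall they report 0.552 and 0.564, odds ratio 0.95. The artefact passes through, much weakened.

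**Against sampling error.** At 60% uptake the 95% half-width is 1.96 x sqrt(0.60 x 0.40/100) = 9.6 points. With 80 and 20 people, a normal approximation gives about 8%, 16% and 41% chance that the odds ratios 0.79, 0.62 and 0.42 reach two-sided 5% significance.

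**The case against.** The strongest reply is that the plan does not ignore objective data. The Approach opening makes them part of the primary outcome, and Data analysis says they will be collected. That stands: a reader might infer that the primary outcome rests wholly on memory, but the documents show two conflicting definitions and no combining rule.

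A reader might also infer that the Aim 2 model uses self-report and that cognition will emerge as a false predictor. The documents support neither step. The source of the Aim 2 outcome is unstated, and the listed covariates are demographic and psychosocial, without AD8. Bias would have to enter through correlates, where the working shows it is smaller. Nor are participants selected for memory loss: they are a community sample aged over 50 with no cognitive entry criterion.

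The recall task is not extreme, since screening is in person with immediate feedback. The item also asks where and why screening was received, which should expose some Yes answers based on the checklist. This reduces the false-Yes risk but does not remove it, because no rule says how such answers are classified.

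Finally, this is an exploratory pilot without a power calculation, the shift in uptake is within sampling error, and a moderate artefact would usually miss significance. That limits the size of the point. It does not answer it, because the estimates are to be published and used in planning a larger trial whether or not they are significant.

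**Conclusion.** The point holds as a defect in outcome definition with a plausible bias, not as a demonstrated one. Two parts of the Approach disagree on the primary outcome, the Aim 2 dependent variable has no named source, and nothing says whether the checklist or the survey AD8 counts as screening. Under the stated forgetting-only assumptions, true uptake of 60% is reported as 53-56% and the AD8 odds ratio is 0.42-0.79 when the truth is 1.0. Other assumed error rates give a ratio above 1 or near 1. A firm statement that reporting error will follow cognition and appear as a barrier would go beyond the documents. It is worth correcting because the better data are already being collected.

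**What to change.** 1. Reconcile the two definitions of the primary outcome in the Approach.
2. Link event records to participant IDs. Anyone may be screened at the events, so an unlinked count cannot serve the 100 participants.
3. Make event-recorded receipt of study screening the 4-month uptake outcome and the Aim 2 dependent variable. Add outside screening from self-report, using the where item and limited to screening since baseline, because the ever/past-year wording reaches further back.
4. Keep self-report for the baseline/4-month comparison. The event record has no baseline counterpart, so it cannot replace self-report there.
5. State in the outcome definition and the survey item that the risk checklist and the AD8 given in the survey do not count as screening.
6. Report agreement between self-report and the event record overall and, descriptively, by baseline AD8.

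The cost is wording, a linkage field and one table. The headline figure may be less favourable, and outside screening stays self-reported. Agreement among AD8-positives will be imprecise: 20 people at 60% uptake leaves 20 x 0.60 = 12 screened, and at 75% recall the half-width is 1.96 x sqrt(0.75 x 0.25/12), about 25 points.
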